4.1 Confidence intervals and P values

The overall type I error rate will be fixed at 0.05. The Hochberg procedure will be used to test each of the two-sided hypothesis tests for the two primary outcomes. The largest of the two P values will be compared to $\alpha = 0.05$, and if this test is non-significant, the smaller P value will be compared to $\alpha/2 = 0.025$. If the largest P value is < 0.05 , both hypothesis tests will be rejected.³⁰ If both of the two primary outcomes are tested at the 0.05 significance level, 95% CIs will be reported; if either of the primary outcomes are tested at the 0.025 significance level, 97.5% CIs will be reported for both tests.

All secondary analyses will be considered exploratory in nature and P values will not be reported; 95% CIs will be reported without adjustment for multiple testing.

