6.1 Outcome definitions and analysis methods

Two primary outcomes

We will assess two outcomes: the between-group difference in 6-month urinary albumin-to-creatinine ratio (log-transformed, measured in mg/mmol), and the 6-month change in eGFR (6-months post-randomization minus pre-randomization, measured in mL/min per 1.73m²). Placebo will serve as the referent group in all analyses.

Albuminuria: Albuminuria will be measured using urinary albumin-to-creatinine ratio from first morning urine samples. At each visit (pre-randomization, and 3- and 6-months post-randomization), urinary albumin-to-creatinine ratio is measured on two consecutive days and the average of the two values will be computed. The average of the two values will be log-transformed using the natural logarithm. A summary of the pre-treatment, 3-month and 6-month urinary albumin-to-creatinine ratio measurements will be provided. The geometric mean ratio of 6-month urinary albumin-to-creatinine ratio will be estimated using linear regression, where the outcome is the log-transformed average of two 6-month follow-up visit urinary albumin-to-creatinine ratio measurements minus log-transformed average of two pre-treatment urinary albumin-to-creatinine ratio measurements, adjusting for a treatment indicator variable and the log-transformed average of two baseline urinary albumin-to-creatinine ratio measurements. The 95% or 97.5% CI for the geometric mean ratio will be presented.³³

eGFR: eGFR will be calculated using the CKD-EPI formula, which includes patient age, sex, race (black vs. other), and the serum creatinine concentration.³⁴ We will summarize the pre-randomization, 3-month and 6-month eGFR measurements by group. We will estimate the between-group difference in change in eGFR (6-month eGFR minus pre-randomization eGFR), expressed in mL/min per 1.73m², using linear regression. The outcome is the change in eGFR (6-month value minus pre-randomization value) and the treatment indicator variable will be included as a covariate. The 95% or 97.5% CI for the between-group difference in change in eGFR will be presented.

Secondary outcomes

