Health-related quality of life: We will summarize health-related quality of life scores determined by the RAND version of the 36-Item Short Form Health Survey (SF-36) administered pre-randomization and at 3-months and 6-months post-randomization. The physical composite summary (PCS) score and mental composite summary (MCS) score of the SF-36 will be examined separately. The between-group difference in change in each composite score, 6-month value minus pre-randomization value, will be reported with 95% CIs. Beyond preservation of kidney function are several other potential mechanisms by which curcumin may benefit quality of life, including potential benefits on depression and chronic pain.^{35,36}

Glycemic control: We will summarize the percentage of glycated hemoglobin pre-randomization and at 3-months and 6-months post-randomization. We will present the between-group difference in change in percentage of glycated hemoglobin (6-month value minus pre-randomization value) among patients with diabetes mellitus (diabetes mellitus was a stratification variable in the randomization), with the 95% CI.

Progressive CKD, ESRD and death: We will report on the outcome of progressive CKD, ESRD, and death, first as a composite outcome, and then as separate components. We will define ESRD as an eGFR <15 mL/min/1.73 m² or the initiation of renal replacement therapy, which includes chronic dialysis or transplantation; progressive CKD will be defined as an eGFR loss of $\geq 30\%$ (anytime during follow-up from the pre-randomization baseline value) or ESRD. We expect less than 10% of participants will experience these outcomes by 6 months. Our focus is to document any trends to inform the expected event rate for future studies. Each outcome (progressive CKD, ESRD and death) will be summarized separately as number (percentage) of patients with the event by group. The HR of progressive CKD (as its own outcome) will be estimated using Cox proportional hazards regression, treating death as a competing event. The same approach will be used for the outcome of ESRD. Each estimate will be reported with 95% CIs.

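### The SF-36 and HbA1c contrasts are planned as differences in change with no baseline covariate: valid, but less precise than a baseline-adjusted analysis of data already collected

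*Combined protocol and SAP*

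**What the plan says.** SAP section 6.1, under Secondary outcomes, defines the effect on the two SF-36 composites in one sentence: "The between-group difference in change in each composite score, 6-month value minus pre-randomization value, will be reported with 95% CIs". For glycemic control it plans the "between-group difference in change in percentage of glycated hemoglobin (6-month value minus pre-randomization value) among patients with diabetes mellitus", again with a 95% CI. Neither sentence names an estimation model or a covariate.

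The baselines exist. The SF-36 is "administered pre-randomization and at 3-months and 6-months post-randomization", and for HbA1c the SAP says: "We will summarize the percentage of glycated hemoglobin pre-randomization and at 3-months and 6-months post-randomization".

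Two other places set the context. SAP section 4.1 limits inference on these outcomes: "All secondary analyses will be considered exploratory in nature and P values will not be reported; 95% CIs will be reported without adjustment" (the adjustment meant there is for multiplicity, not for baseline). And where the SAP wants baseline adjustment it writes it out: the albuminuria outcome is a change in log ratio, estimated by linear regression "adjusting for a treatment indicator variable and the log-transformed average of two baseline urinary albumin-to-creatinine ratio measurements".

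**The concern.** A simple change score subtracts the whole baseline value from the follow-up value, which fixes the baseline slope at 1. When the true slope is below 1, this subtracts too much. Noise is added to the contrast, and a chance difference between arms at baseline is over-corrected. Regression on the baseline value estimates the slope from the data and, in large samples, is never less precise than the change score.

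Since no P values will be given, the position and width of these intervals are the whole result on quality of life and glycemic control, the first two secondary objectives in SAP section 2.2. SAP section 6.1 itself warns that a trial of this size may show imbalances on characteristics that influence outcomes. HbA1c is analysed only in patients with diabetes. Stratifying on diabetes status balances their numbers between arms, not their HbA1c levels.

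**Working it through.** **The plan's own figures.** None is stated for SF-36 or HbA1c: no SD, correlation, interval width or power. The nearest are the primary-outcome powers in SAP section 3.3, which also fix the number per arm: 518 × 0.95 / 2 = 246. Using power = Φ(δ / (SD·√(2/n)) − 2.241) at two-sided alpha 0.025:

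- Albuminuria: δ = |ln 0.75| = 0.288, SD 1.0, gives 82.9% (stated 82%).
- eGFR: δ = 1.65, SD 5.8, gives 82.0% (stated 81%).

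Both reproduce to within about a point, so 246 per arm is a fair basis for the whole-trial SF-36 contrasts. It does not apply to HbA1c, because the documents do not give the number of patients with diabetes.

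**Which reading of section 6.1 is natural.** The published protocol (Statistical Methods, Secondary outcomes) used a two-sample t test on HbA1c change. The SAP's eGFR model, also on change, contains only the treatment indicator. The covariate-adjusted sensitivity analyses in SAP section 6.1 cover the two primary outcomes only, and section 6.3 plans nothing further. The unadjusted difference in change is therefore the natural reading, and nothing elsewhere supplies the adjustment.

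**Width under equal SDs.** Let s be the common SD and r the baseline to 6-month correlation. Both are assumptions.

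- Change-score variance: 2s²(1 − r)
- Baseline-adjusted variance: s²(1 − r²)
- Planned width / adjusted width = √(2 / (1 + r))
- Equivalent extra patients per arm (SF-36 only) = 246 × (2/(1 + r) − 1)

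| r (assumed) | Planned CI wider by | Adjusted CI narrower by | Extra per arm, SF-36 |
|---|---|---|---|
| 0.4 | 19.5% | 16.3% | 105 |
| 0.5 | 15.5% | 13.4% | 82 |
| 0.6 | 11.8% | 10.6% | 62 |
| 0.7 | 8.5% | 7.8% | 43 |
| 0.8 | 5.4% | 5.1% | 27 |
| 0.9 | 2.6% | 2.5% | 13 |

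**Simulation check.** In 1,500 simulated trials of 246 per arm for each r, the planned interval was 11.7%, 8.4% and 5.3% wider at r = 0.6, 0.7 and 0.8, in line with the formula. Coverage was about 94% to 96% for both methods.

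**Unequal SDs.** With k = SD at 6 months / SD at baseline, the width ratio is √[(1 + k² − 2rk) / (k²(1 − r²))]. Over r = 0.5 to 0.9 the excess width is 11% to 22% at k = 0.9, and 0% to 11% at k = 1.1. The loss vanishes when the true slope rk equals 1.

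**Illustration in SF-36 points.** Assume r = 0.6 and SD 10.

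- Planned: SD of change = 10√0.8 = 8.94, so the half-width is 1.96 × 8.94 × √(2/246) = 1.58.
- Adjusted: residual SD = 10√0.64 = 8.00, so the half-width is 1.41.
- Half-widths scale with the SD: 1.26 and 1.13 at SD 8, 1.90 and 1.70 at SD 12.

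**Chance imbalance.** Given a baseline difference D between arms, the change-score contrast is shifted by (rk − 1)·D. With r = 0.6 and k = 1 that is −0.4D, so a 1-point imbalance shifts the estimate by 0.4 points in the opposite direction.

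**The case against.** The strongest reply is that nothing is invalid. Under randomization the difference in change is unbiased, its interval covers as it should, and the outcomes are labelled exploratory. Progression to a larger trial rests on albuminuria or eGFR, not on SF-36 or HbA1c. In the illustration the gain is 0.17 points of half-width (1.58 − 1.41). All of this stands, and it sets the severity.

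A second reply is that the SAP names a quantity, not a model. The albuminuria analysis shows that an outcome defined as a change can also be baseline-adjusted, so adjustment is unspecified here and not excluded. That is fair. It does not remove the need to act: two valid estimators would give different estimates and intervals from the same data, and a SAP should choose between them in advance.

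Some stronger readings are tempting but not supported:

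- A reader might infer that the SAP ignores baseline. It does not: a change score uses baseline with a fixed slope, and pre-randomization data enter the imputation models.
- A reader might take a given percentage loss as established. With neither r nor the SD ratio in the documents, the loss could be near zero.
- A reader might apply the 246-per-arm figures to HbA1c, or conclude that the loss exceeds that for the unadjusted eGFR model. The documents give no numbers for either step.

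**Conclusion.** The point holds as one of efficiency and of sensitivity to chance imbalance, not of bias or coverage. That adjustment does not lose precision in large samples is independent of the assumed correlation. The size is not: about 15% to 5% excess width rests on equal SDs, complete data and r between 0.5 and 0.8, and it shifts in either direction with the SD ratio. Severity is minor. It is worth acting on because the improvement is free and because these intervals carry all the planned inference on three secondary measures.

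**What to change.** In SAP section 6.1, state that each of the three contrasts (SF-36 physical composite, SF-36 mental composite, HbA1c in patients with diabetes) is estimated by linear regression of the 6-month value, or equivalently the change, on treatment and the pre-randomization value of the same measure. Report the treatment coefficient with its 95% CI, combined across imputations as already planned. Keep the by-group summaries of change as description.

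The cost is one model term in three secondary analyses and a line in Supplemental Table 1, made before treatment allocation is revealed. No new data are needed, the target remains a difference in means, and the method matches the one already chosen for albuminuria.

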2.2 Objectives

Our primary objective is to assess the between-group difference in two outcomes examined separately: urinary albumin-to-creatinine ratio (6-month post-randomization value) and change in eGFR from pre-randomization to 6-months post-randomization.

Our secondary objective is to assess: i) the between-group difference in health related quality of life (as assessed by a 6-month change in the RAND version of the 36-Item Short Form Health Survey [SF-36]), ii) the between-group difference in glycemic control (as assessed by a 6-month change in glycated hemoglobin among patients with diabetes mellitus; diabetes mellitus was a stratification variable in the randomization), iii) the risk of a composite outcome of progressive CKD, ESRD or death with micro-particle curcumin versus placebo, and iv) the between-group difference in measured serum levels of curcumin and its major metabolites (to be done on measurements taken 3-months after randomization in the first 30 participants; being done to assess curcumin bioavailability).^{14,16}

We will also conduct a pre-specified exploratory subgroup analysis of the primary outcomes based on a higher or lower estimated risk of future kidney failure (based on the kidney failure risk equation¹⁹).

3. Study Methods

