In our preliminary work on urinary albumin-to-creatinine ratio testing, we found patients eligible for MPAC-CKD-1 had a mean initial urinary albumin-to-creatinine ratio of 128.3 mg/mmol.²⁶ Over 3 months, we observed a mean increase in the urinary albumin-to-creatinine ratio of 30.7 mg/mmol and found the standard deviation of the change to be 69.2 mg/mmol. Enrolling a total of 518 patients and

accounting for 5% loss to follow-up allows for 82% power ($\alpha = 0.025$) to detect a geometric mean ratio of 0.75, assuming a standard deviation of the 6-month log-transformed albumin-to-creatinine ratio of 1.0.²⁷ For the between-group difference in change in eGFR (6-month eGFR minus pre-randomization eGFR), we will have 81% power ($\alpha = 0.025$) to exclude a difference of 1.65 mL/min per 1.73 m² between treatment and control groups (using a standard deviation of the change of 5.8 mL/min per 1.73 m²). In general, the average decline in eGFR in albuminuric CKD patients is 2 to 4 mL/min per 1.73 m² per year (with a standard deviation of 3-4 mL/min per 1.73 m² per year).^{28,29} The standard deviations used in these sample size calculations are based on overall standard deviations observed in the MPAC-CKD-1 study.

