Serum curcumin levels: To confirm our micro-particle curcumin was bioavailable,¹⁶ and to strengthen any relationship between micro-particle curcumin and any outcomes we identify, serum levels of curcumin and its major metabolites were measured in the first 30 participants 3 months after randomization (including patients taking micro-particle curcumin and those taking placebo). Serum curcumin and its major metabolites will be summarized in the first 30 participants randomized, by group. The between-group difference in average serum curcumin levels measured 3-months post-randomization will be reported with the 95% CI.

Pre-specified subgroup analysis

We will conduct an exploratory subgroup analysis based on a higher or lower estimated risk of kidney failure, using the kidney failure risk equation.¹⁹ Participants with a 2-year risk of ESRD less than 10% will be classified as lower risk, and patients with a risk of 10% or more will be classified as higher risk. For both primary outcomes, separate regression models with an interaction term between randomization group and the kidney failure risk category indicator variable will be used. The 6-month albumin-to-creatinine ratio geometric mean ratio will be reported for each kidney failure risk equation group, and the difference in change in eGFR will be reported for each kidney failure risk group, along with 95% CIs.

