Missing data for reasons other than death will be handled using model-based multiple imputation methods (as the primary method to handle missing data in all analyses). Additional analyses will be performed to confirm that conclusions are not sensitive to assumptions about the missing-data mechanism.³⁷ In the primary analyses, outcomes that are missing due to death will not be imputed (expected in less than 5% of patients). In sensitivity analyses, to account for missing values due to death we will (i) use multiple imputation to impute missing outcomes; (ii) use single imputation where a missing 6-month albumin-to-creatinine ratio will be imputed as a doubling of the baseline albumin-to-creatinine ratio value, and 6-month eGFR will be imputed as half of the pre-randomization eGFR. Pre-randomization data, the treatment variable, stratification variables, and data collected at both the 3-month and 6-month visits will be included in the multiple imputation models. For patients missing both urinary albumin-to-creatinine ratio measurements at a particular visit, one urinary albumin-to-creatinine ratio will be imputed as the average value; urinary albumin-to-creatinine ratio will be imputed on the log scale. If a patient is missing one of the two urinary albumin-to-creatinine ratio measurements at a particular visit, the single observed value will be taken as the average urinary albumin-to-creatinine ratio for that visit and no imputation will occur. Estimates from each complete dataset will be combined using standard methods.³⁸ The imputation model will allow for an interaction effect between the treatment variable and the kidney failure risk equation indicator variable.³⁹

For all primary and secondary outcomes, the pre-randomization, 3-month and 6-month measurements will be summarized by group as mean (standard deviation) and median (25th and 75th percentiles) or number and percentage, depending on whether the variable is continuous or categorical.

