6.3 Additional analyses

No additional analyses are planned.

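### Kidney failure risk enters the only subgroup analysis as a 10% indicator; if the effect changes smoothly with risk, a continuous interaction would keep information that the cut loses

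*Combined protocol and SAP*

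**What the plan says.** SAP 2.2 announces the analysis: "We will also conduct a pre-specified exploratory subgroup analysis of the primary outcomes", by estimated risk of future kidney failure. The published protocol (Other analyses) names the kidney failure risk equation but gives no cut. SAP 6.1 supplies one: "Participants with a 2-year risk of ESRD less than 10% will be classified as lower risk". Everyone at or above that value forms the other category. This two-level variable is the only form in which risk meets treatment in the models for UACR and eGFR: "separate regression models with an interaction term between randomization group and the kidney failure risk category indicator variable will be used". Each category then gets its own effect estimate and 95% CI.

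The missing-data text in SAP 6.1 carries the split forward: "The imputation model will allow for an interaction effect between the treatment variable and the kidney failure risk equation indicator variable". SAP 6.3 closes the list: "No additional analyses are planned". On reporting, SAP 4.1 says: "All secondary analyses will be considered exploratory in nature and P values will not be reported".

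The documents give no distribution of the risk score, no expected share of patients on either side of 10%, no reason for that cut, and no precision or power for the interaction.

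**The concern.** The risk equation returns a number for each patient. Reducing it to an indicator treats patients at 9% and 11% as different, and patients at 11% and 60% as the same. Eligibility covers eGFR from 15 to 60 with no upper limit on albuminuria, so risk within one category could vary widely. If the effect rises or falls gradually with risk, an indicator captures only part of that gradient. If few patients lie on one side of the cut, the estimate for that side will also be imprecise.

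This is the only planned look at effect modification, and it will be read through confidence intervals, so precision is what is at stake. A continuous interaction added after the results are known would be post hoc. It would also rest on imputations whose treatment-by-risk interaction was specified only for the indicator.

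**Working it through.** **Inputs from the documents (SAP 3.3, 3.1, 4.1).** 518 patients, 5% loss, 1:1 allocation, two-sided alpha 0.025. Log UACR: SD 1.0, geometric mean ratio 0.75. eGFR change: SD 5.8, difference 1.65.

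**Step 1: the plan's own figures.** Evaluable patients: 518 × 0.95 ≈ 492, or 246 per arm.
- UACR: SE = 1.0 × √(2/246) = 0.0902. |ln 0.75| / 0.0902 = 3.19. Power = Φ(3.19 − 2.24) ≈ 82.9% (82.7% with the noncentral t). The SAP states 82%.
- eGFR: SE = 5.8 × √(2/246) = 0.523. 1.65 / 0.523 = 3.155. Power ≈ 82.0% (81.7% with t). The SAP states 81%.

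The stated powers reproduce. There is no stated figure for the subgroup analysis to reproduce.

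**Step 2: information kept by a cut.** For an interaction linear in a score X, the share kept by an indicator I is corr(X, I)². If X is normal with proportion p on one side of the cut, this equals φ(z_p)² / [p(1 − p)].

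| Split | Kept | Lost | Equivalent patients, of 492 |
|---|---|---|---|
| 50/50 | 0.637 | 36% | 313 |
| 70/30 | 0.576 | 42% | 283 |
| 80/20 | 0.490 | 51% | 241 |
| 90/10 | 0.342 | 66% | 168 |
| 95/5 | 0.224 | 78% | 110 |

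For example, at 80/20: z = 0.842, φ(z) = 0.280, and 0.280² / 0.16 = 0.490.

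**Step 3: other assumptions.**
- Uniform score, linear interaction: loss of 25% at 50/50, 37% at 70/30, 52% at 80/20, 73% at 90/10.
- Normal log-odds (SD 0.8 to 1.6) with the effect linear in raw risk, and 10% to 50% of patients above the cut: loss of about 37% to 51%.
- Effect that steps exactly at 10%: no loss.

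**Step 4: does the shape matter?** Simulation of 4,000 trials of 492 patients, residual SD 1, two-sided 0.05. The interaction size is an assumption: 0.25 residual SD per SD of the true modifier.

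| Split | True shape | Power, continuous term | Power, indicator |
|---|---|---|---|
| 50/50 | linear | 79% | 59% |
| 50/50 | step at cut | 60% | 79% |
| 70/30 | linear | 79% | 54% |
| 70/30 | step at cut | 53% | 79% |
| 90/10 | linear | 78% | 36% |
| 90/10 | step at cut | 35% | 77% |

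Each form does better when its own shape is true.

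**Step 5: width of a category estimate.** Half-width = 1.96 × 2 × SD / √n, with the SAP's SDs. The shares are assumptions.
- 20% in the smaller category (n ≈ 98): a ratio of 0.75 would have a 95% CI of about 0.51 to 1.11, and the eGFR half-width would be about 2.3.
- 10% (n ≈ 49): about 0.43 to 1.31, and about 3.2.

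The UACR intervals are on the wide side, because the UACR model adjusts for baseline and its residual SD should be below 1.0.

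**The case against.** The strongest defence is that the split is pre-specified, labelled exploratory, and leaves the primary analyses untouched. It gives a directly readable effect in each risk group without assuming linearity, and step 4 shows that it outperforms a linear term if there is a true threshold at 10%. All of that stands. It is why the split should be kept, and why a reader should not infer that dichotomizing has no benefit.

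Three other stronger readings are tempting and are not supported:
- That the cut simply discards 36% to 66% of the information. That range needs a roughly normal score, a linear interaction, and a smaller group of 10% to 50%. The documents establish none of these.
- That this subgroup would decide whom to enrol in MPAC-CKD-2. The documents tie the larger trial to an effect on either primary marker and to feasibility, tolerability and event rates. They never tie it to risk category.
- That the imputation model sees risk only as an indicator. SAP 6.1 also puts pre-randomization data, the stratification variables and both follow-up visits into it. Only the treatment-by-risk interaction is named in dichotomized form.

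Nor can the analysis be called underpowered on the documents alone. No interaction size is given and no interaction P value is planned.

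**Conclusion.** The point holds in conditional form. The sole effect-modification analysis uses kidney failure risk only as a 10% indicator. If the effect is linear in a roughly normal log-odds score, this loses about 36% (50/50), 51% (80/20) or 66% (90/10) of the interaction information. Under the other smooth assumptions tried, and allowing a 95/5 split, the loss runs from about 25% to 78%. Under a true step at 10% it is zero. The actual split and the shape of any effect modification are not in the documents. The SAP offers no reason to expect a step at 10%, so planning for both shapes is prudent. This is an optional improvement to an exploratory analysis, not a flaw in the primary inference.

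**What to change.** In SAP 6.1, before treatment allocation is revealed:

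1. Keep the estimates below 10% and at 10% or more, and report the number of patients in each category by arm.
2. For each primary outcome, add a model with treatment, log-odds of predicted 2-year risk, and their interaction. Report the treatment effect with 95% CI at the 25th, 50th and 75th percentiles of risk.
3. Check linearity with a spline in risk and its interaction with treatment.
4. In the imputation model, keep the indicator interaction and add treatment by continuous risk, so that imputation and analysis agree.

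The cost is a few sentences, one added model per outcome and one added imputation term. No new data are needed, since the risk must be calculated anyway to form the categories. The downside is a linearity assumption on the log-odds scale, which step 3 checks and the retained categories complement.

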3.2 Randomization

Balanced block randomization was conducted using a computerized algorithm with variable block sizes; treatment allocation was stratified by site (3 sites in London, 1 site in Hamilton) and by the presence or absence of baseline diabetes mellitus. After providing written informed consent, patients were allocated randomly by means of a 24-hour online computerized system to maintain allocation concealment. Participants, investigators, and all research staff are unaware of the treatment allocation. Unblinding could have occurred in the setting of a severe adverse reaction in which the treating physician believed the investigational product may have had a role in the patient's condition or treatment. Unblinding events will be summarized by group.

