Randomization reliably removes random differences between treatment groups when at least 1000 participants are included.⁴⁰ With the size of our sample, it is possible that imbalances may arise between the treatment groups on important characteristics that may influence outcomes. In sensitivity analyses, we will repeat the two primary analyses while (i) accounting for randomization strata (centre and pre-randomization diabetes); (ii) accounting for randomization strata and adjusting for variables associated with disease progression including age, sex, tobacco use, blood pressure, baseline use of angiotensin-converting enzyme inhibitors or angiotensin receptor blockers, and baseline use of aldosterone antagonists. We do not anticipate that accounting for randomization strata and/or adjustment for pre-randomization variables will change the results in any meaningful way.

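### Randomization was blocked within site and diabetes, but both primary models omit these factors, so the primary standard errors are slightly too large to the extent that the strata predict the outcomes (minor)

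*Combined protocol and SAP*

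**What the plan says.** - **Randomization (SAP 3.2; also Protocol, Interventions).** Balanced blocks of variable size were used, and "treatment allocation was stratified by site (3 sites in London, 1 site in Hamilton) and by the presence or absence of baseline diabetes mellitus". This gives 4 × 2 = 8 strata.
- **Primary eGFR model (SAP 6.1).** The outcome is the 6-month change. Of the covariates, the SAP says only that "the treatment indicator variable will be included as a covariate".
- **Primary UACR model (SAP 6.1).** The outcome is the change in log UACR, "adjusting for a treatment indicator variable and the log-transformed average of two baseline urinary albumin-to-creatinine ratio measurements". Neither site nor diabetes appears.
- **Sensitivity analyses (SAP 6.1).** "In sensitivity analyses, we will repeat the two primary analyses while (i) accounting for randomization strata (centre and pre-randomization diabetes"), and then (ii) with further baseline covariates. The SAP adds: "We do not anticipate that accounting for randomization strata and/or adjustment for pre-randomization variables will change the results in any meaningful way".
- **Imputation models (SAP 6.1).** The listed content is "Pre-randomization data, the treatment variable, stratification variables, and data collected at both the 3-month and 6-month visits", so the strata are already used there.
- **Decision rule (SAP 4.1).** The Hochberg procedure is applied to the two primary tests, and the 95% or 97.5% intervals follow from the level at which those tests are made.

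**The concern.** When allocation is blocked within strata, the arms are nearly balanced on those strata by design. Outcome variation between strata then contributes almost nothing to the variance of the treatment difference. A regression that omits the strata leaves that variation in its residual, so its reported standard error exceeds the true one.

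The SAP motivates adjustment by the possibility of chance imbalance. For site and diabetes that is not the main reason, because blocking already limits imbalance on them. The reason to model them is to obtain a standard error that matches the design, and that argument applies to the primary analysis. The planned sensitivity analyses will show strata-adjusted estimates, but they do not alter the P values entering the Hochberg step or the primary intervals.

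What is at stake is a little precision. To the extent that the strata predict outcome, the primary intervals are wider and the primary tests more conservative than the design warrants.

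**Working it through.** **Inputs (SAP 3.3 and 4.1).** N = 518 with 5% loss, so 518 × 0.95 / 2 ≈ 246 per arm. Two-sided α = 0.025, so z = 2.2414. For eGFR the difference is δ = 1.65, "using a standard deviation of the change of 5.8 mL/min per 1.73" m². For UACR the geometric mean ratio is 0.75 and the log-scale SD is 1.0.

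**Reproducing the stated power (normal approximation)**
- eGFR: SE = 5.8 × √(2/246) = 0.523; δ/SE = 3.155; power = Φ(3.155 − 2.241) = 82.0% (SAP: 81%).
- UACR: SE = √(2/246) = 0.0902; |ln 0.75|/SE = 3.19; power = 82.9% (SAP: 82%).
- The eGFR 97.5% interval half-width is 2.2414 × 0.523 = 1.17 mL/min/1.73 m².

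Both agree with the SAP to within about one point. The stated power is not in question.

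**How much could the strata explain?** The documents give no R², so it has to be assumed.

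*Diabetes, eGFR.* With prevalence p and a 6-month difference D between diabetic and other patients, R² = p(1 − p)D²/5.8². SAP 3.3 says "the average decline in eGFR in albuminuric CKD patients is 2 to 4 mL/min per 1.73" m² per year. It does not split this by diabetes, so the following splits are assumptions, as is p = 30 to 70%.
- Losses of 4 versus 2 per year (D = 1): R² = 0.62% at p = 0.3 or 0.7, and 0.74% at p = 0.5.
- Losses of 4 versus 0 per year (D = 2, extreme): R² = 2.50% and 2.97%.
- At p = 0.5, R² of 5% or 10% through diabetes alone would need D = 2.6 or 3.7. That exceeds the whole average 6-month decline of 1 to 2.

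*Site, eGFR.* If one site held an assumed 25% of patients and alone differed, D = √(R² × 5.8²/(0.25 × 0.75)). R² of 1, 2 or 5% would need D = 1.3, 1.9 or 3.0.

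**Consequence for eGFR.** Let k = √(1 − R²).
- Overstatement of SE = 1/k − 1
- Actual size = 2[1 − Φ(z/k)]
- Power without strata = Φ((δ/SE − z)/k)
- Power with strata = Φ(δ/(SE·k) − z)
- Narrowing of the half-width = 1.17 × (1 − k)

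| R² | SE too large by | Actual size at nominal 0.025 | Power without / with strata | Half-width falls by |
|---|---|---|---|---|
| 0.74% | 0.4% | 0.0245 | 82.0 / 82.3% | 0.004 |
| 3% | 1.5% | 0.0229 | 82.3 / 83.2% | 0.018 |
| 5% | 2.6% | 0.0215 | 82.6 / 84.0% | 0.030 |
| 10% | 5.4% | 0.0181 | 83.2 / 86.1% | 0.060 |

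**Simulation check of the eGFR model.** N = 492, 4 sites × diabetes, 10,000 trials per setting. Blocks of 4 and 6, site shares of 30/25/20/25% and 50% diabetes are assumed. Each pair is without / with strata.
- R² = 0.74% (diabetes only): mean reported SE 0.522 / 0.521; power 81.8 / 81.9%; size 0.0252 / 0.0256. With a Monte Carlo SE of 0.0016 for size, no difference is detectable.
- R² = 2.97% (diabetes only): SE 0.523 / 0.515; power 81.8 / 82.8%; size 0.0228 / 0.0245.
- R² = 2.74% (diabetes 0.74% plus one site 2%): SE 0.523 / 0.515; power 81.8 / 82.6%; size 0.0230 / 0.0246.

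**UACR.** The same ratios 1/k apply, with R² now the share of the variance left after baseline log UACR that the strata explain. The documents give nothing from which to set it. No power gain is claimed, because the SD of 1.0 in SAP 3.3 is for the 6-month log value, whereas the primary model already adjusts for baseline.

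**Cost in degrees of freedom.** Four extra terms (3 for site, 1 for diabetes) move the critical t at two-sided 0.025 from 2.2483 to 2.2484.

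**The case against.** The strongest reply is that the matter is already handled and too small to report. The strata-adjusted analysis is pre-specified, Supplemental Table 1 records it as a considered change, and readers will see both results. In the best-supported eGFR case the effect cannot be seen in simulation. A standard error on about 490 degrees of freedom has sampling error of roughly 1/√(2 × 490) = 3.2%, well above an overstatement of 0.4 to 1.5%. The rows at 5 and 10% have no support in the documents, and standardized central hospital laboratory methods (Protocol, Data Collection Methods) make large site differences less likely. There is also a cost in continuity: the eGFR model was chosen to be practically equivalent to the published t test, and the UACR model to follow a published method. This would be a second change to the primary models, close to the final analysis and after pooled SDs from the trial had been examined.

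Much of this stands. The effect is small, R² is unknown, and the upper rows only bound the range. It does not remove the point. The sensitivity analyses do not feed the primary decision. The overstatement is systematic, whereas sampling error in the SE averages out. That the adjusted model is already specified makes exchanging the two easy. The credibility cost is real, and is why the change is worth making only before results are known and with a dated record.

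**Conclusion.** The concern holds, as a minor one. The primary models do not reflect the stratified randomization, and to the extent that the strata predict outcome their standard errors are too large. The consequence is conservative: no bias, no inflated type I error, and no error in the stated 82% and 81% power. If the strata predict nothing, nothing is lost.

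For eGFR the likely gain from adjustment is under one power point, with the 97.5% half-width of 1.17 narrowing by about 0.004 to 0.018 mL/min/1.73 m². This rests on assumed values for diabetes prevalence, the difference in decline by diabetes, and site effects. For UACR the benefit is a correctly calibrated standard error of unknown size. The direction is certain; the magnitude is an assumption.

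**What to change.** In SAP 6.1, before unblinding, add site (4 levels) and baseline diabetes (yes/no) as fixed effects to both primary regression models. Keep the models without strata as a sensitivity analysis in place of item (i). Item (ii) can stay as it is.

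Record the dated change and its reason in the primary-analysis and sensitivity-analysis rows of Supplemental Table 1. State that it was made without knowledge of the trial results, as section 6 states for the existing changes. If results by group are already known, leave the primary models as they are.

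The cost is a few lines of text and 4 of about 490 degrees of freedom. No new data are needed: both factors were recorded for randomization and are already in the imputation models.
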